## **Appendix 3. ENDPOINT DEFINITION AND DATA DERIVATION DETAILS**

#### 1. ACR Assessments

The American College of Rheumatology's definition for calculating improvement in RA (ACR50) is calculated as a  $\geq$  50% improvement in tender and swollen joint counts and  $\geq$  50% improvement in 3 of the 5 remaining ACR-core set measures: patient and physician global assessments, pain, disability, and an acute-phase reactant. Similarly, ACR20 and ACR70 are calculated with the respective percent improvement. This efficacy measurement will be made at every study visit. The specific components of the ACR Assessments that will be used in this study are:

- 1) Tender/Painful Joint count (68);
- 2) Swollen Joint Count (66);
- 3) Patient's Assessment of Arthritis Pain (VAS);
- 4) Patient's Global Assessment of Arthritis (VAS);
- 5) Physician's Global Assessment of Arthritis (VAS);
- 6) C-Reactive Protein (CRP);
- 7) Health Assessment Questionnaire Disability Index (HAQ-DI).

If the value in any of the components at a timepoint is missing, the component variables that are not missing will be used to determine the response status. As a general principle, if there are sufficient non-missing components to determine whether the ACR endpoint is a response or non-response, then ACR endpoint is not missing, else if the available non-missing components are not sufficient to determine the response status of ACR endpoint then it is considered missing.

In order to avoid numerical difficulty, if the baseline value of any component is equal to 0, the following algorithm will be used in evaluating the percent change from baseline:

- If change from baseline is also equal to 0, then percent change from baseline is set to be 0%;
- If change from baseline is > 0, then percent change from baseline is set to be 999999%.

These percentages will be used to derive the ACR endpoints. Change from baseline cannot be < 0 since none of the components should have negative value.

The swollen joint and tender/painful joint counts will be calculated per Section 9 and Section 10 of Appendix 3.

Lower limit of quantification (LLOQ) for CRP is 0.020 mg/dL (or 0.200 mg/L). Any CRP value below the LLOQ will be reported as "< 0.020" in database and will be set to 0.019

mg/dL. The unit for CRP will be mg/dL or mg/L depending on endpoint of interest. The normal range for the CRP is  $\leq 2.87$  mg/L.

The VAS data will need to be rescaled prior to any calculation (Section 3).

#### 2. Health Assessment Questionnaire – Disability Index (HAQ-DI)

The HAQ-DI assesses the degree of difficulty a subject has experienced during the past week in 8 domains of daily living activities: dressing and grooming, arising, eating, walking, hygiene, reach, grip, and other activities. Each activity category consists of 2-3 items. For each question in the questionnaire, the level of difficulty is scored from 0 to 3 with 0 representing "no difficulty", 1 as "some difficulty", 2 as "much difficulty", and 3 as "unable to do". The domain score for each domain is the maximum (i.e., worst) of the scores from the items/questions within the domain. If this domain score is  $\geq$  2, no further adjustment is needed. If it is < 2 (i.e., 0 or 1) but no aids, devices or help from another person is indicated, then also no adjustment is needed. However, if it is < 2 and any aid, device or help from another person is indicated, then it is further adjusted upward to 2 as described below.

Any activity that requires assistance from another individual or requires the use of an
assistive device adjusts to a minimum score of 2 to represent a more limited functional status.

Domain	If domain score is either 0 or 1, adjust to 2 when the following is satisfied.
Dressing and grooming	"Devices used for dressing (button hook, zipper pull, long-handled shoe horn, etc.)" or help from others on "Dressing and Grooming" is checked
Arising	"Special or built up chair" or help from others on "Arising" is checked.
Eating	"Built up or special utensils" or help from others on "Eating" is checked.
Walking	"Cane", "Walker", "Crutches", "Wheelchair", or help form others on "Walking" is checked
Hygiene	"Raised toilet seat", "Bathtub bar", "Long- handled appliances in bathroom", "Bathtub seat" or help from others on "Hygiene" is checked.
Reach	"Long-handled appliances for reach" or help from others on "Reach" is checked
Grip	"Jar opener (for jars previously opened)" or help from others on "Gripping or opening things" is checked.
Activities	Help from others on "Errands and chores" is checked.

Note: For "Other, (specify)", whether checked or unchecked or specifying the other "aids or devices" in this category, is not to be used in the adjustment of the domain score.

For each domain, the domain score will be determined by non-missing scores from the questions. A domain score will only be missing if all scores within the domain are missing. The HAQ-DI score is the average of all the 8 domain scores. If > 2 domain scores are missing, HAQ-DI score is considered missing, else the HAQ-DI score is computed as the average of the non-missing domain scores (Bruce & Fries, 2005). A higher score represents a more limited physical functional status/ability.

## 3. PsA Response Criteria (PsARC)

The PsARC will be calculated at all study visits in addition to the ACR response criteria. The PsARC consists of 4 measurements:

- 1) Tender joint count (68);
- 2) Swollen joint count (66);
- 3) Physician's Global Assessment of Arthritis (VAS);
- 4) Patient's Global Assessment of Arthritis (VAS).

The same tender/painful joint count and swollen joint count used for ACR response criteria will be applied to the PsARC. In order to be a 'PsARC responder', subjects must achieve improvement in 2 of 4 measures, one of which must be joint pain or swelling, without worsening in any measure.

Specifically, the PsARC response is defined as improvement in two of the following 4 criteria, one of which must be joint pain or swelling, without worsening in any measure:  $(1) \ge 20\%$  improvement in Physician's Global Assessment of Arthritis (VAS);  $(2) \ge 20\%$  improvement in Patient's Global Assessment of Arthritis (VAS);  $(3) \ge 30\%$  improvement in tender joint count (68); and  $(4) \ge 30\%$  improvement in swollen joint count (66) (Gottlieb et al, 2008).

Methods for calculating percent change from baseline when baseline value of any component is equal to 0 can be found in Appendix 3 Section 1.

If values in any of the components at a timepoint were missing, the component variables that were not missing were used to determine the response status. It should be noted that since PsARC response requires no worsening in any measure, a subject with any missing components cannot be a responder at that timepoint. If one could not determine the response status in the presence of missing components at the timepoint, then the PsARC response will be considered as missing. Handling of missing values for a subject at timepoint in analyses is found in Section 5.3.

The swollen joint and tender/painful joint counts will be calculated per Section 9 and Section 10 in Appendix 3.

The VAS data will need to be rescaled prior to any calculation (Section 3).

# 4. Physician Global Assessment (PGA) of Psoriasis (PGA-PsO)

The Physician Global Assessment of Psoriasis is scored on a 5-point scale, reflecting a global consideration of the erythema, induration and scaling across all psoriatic lesions. Average erythema, induration and scaling are rated separately over the whole body according to a 5-point severity scale, scored as 0 (none), 1, 2, 3, or 4 (most severe), The severity rating scores are summed and the average taken – the total average is rounded to the nearest whole number score to determine the PGA. See study protocol for additional details.

PGA-PsO response is defined for a subject who achieves a PGA-PsO score of clear (0) or almost clear (1) and a  $\geq$  2-step improvement from baseline.

# 5. Psoriasis Area and Severity Index (PASI)

The Psoriasis Area and Severity Index (PASI) quantifies the severity of a subject's psoriasis based on both lesion severity and the percentage of body surface area (BSA) affected. PASI is a composite scoring by the investigator of degree of erythema, induration, and scaling (each scored separately) for each of four body regions, with adjustment for the percent of BSA involved for each body region and for the proportion of the body region to the whole body. Note: PASI should only be performed if  $\geq 3\%$  of subject's BSA is affected at baseline.

- Lesion severity: The basic characteristics of psoriatic lesions erythema, induration and scaling provide a means for assessing the severity of lesions. Assessment of these three main signs is performed separately for four areas of the body: head and neck, upper limbs, trunk (including axillae and groin), and lower limbs (including buttocks). Average erythema, induration and scaling are rated for each body area according to a 5-point scale: 0, no involvement; 1, slight; 2, moderate; 3, marked; 4, very marked.
- Body surface area involvement (%BSA): The extent (%) to which each of the four areas of the body is affected by psoriasis is assigned a numerical score according to the following area scoring criteria: 0, no involvement; 1, > 0 to 9%; 2, 10 to 29%; 3, 30 to 49%; 4, 50 to 69%; 5, 70 to 89%; 6, 90 to 100%.

In each area, the sum of the severity rating scores for erythema, induration and scaling is multiplied by the score representing the percentage of this area involved by psoriasis, multiplied by a weighting factor (head 0.1; upper limbs 0.2; trunk 0.3; lower limbs 0.4). The sum of the numbers obtained for each of the four body areas is the PASI.

PASI = 0.1Ah (Eh + Ih + Sh) + 0.2Au (Eu + Iu + Su) + 0.3At (Et + It + St) + 0.4Al (El + Il + Sl)

Where A = area of involvement score; E = erythema; I = inducation; S = scaling; h = head; u = upper limbs; t = trunk; l = lower limbs.

The PASI score can vary in increments of 0.1 units from 0.0 to 72.0, with higher scores representing increasing severity of psoriasis.

Each PASI clinical signs component score can be computed as:

- $PASI_E = 0.1Ah (Eh) + 0.2Au (Eu) + 0.3At (Et) + 0.4Al (El)$
- $PASI_I = 0.1Ah (Ih) + 0.2Au (Iu) + 0.3At (It) + 0.4Al (Il)$
- $PASI_S = 0.1Ah (Sh) + 0.2Au (Su) + 0.3At (St) + 0.4Sl (Sl)$

Any missing component will result in PASI as missing.

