#### **3.3. Other Endpoints**

#### 3.3.1. Other Efficacy Endpoints

- $\Delta DAS28-3(CRP)$  at all timepoints;
- Physician's Global Assessment of Psoriatic Arthritis (ΔPGA-PsA) at Month 1, Month 3 and Month 6;
- Percent change from baseline (%∆) in PASI and PASI clinical sign component scores at Month 1, Month 3 and Month 6 for subjects with baseline BSA ≥ 3% and baseline PASI > 0;
- $\% \Delta BSA$  at Month 1, Month 3 and Month 6 for subjects with baseline BSA > 0%;
- Nail Psoriasis Severity Index (ΔNAPSI) Score at Month 1, Month 3 and Month 6 for subjects with baseline NAPSI > 0.

This is a score ranging from 0-8 based on 1 targeted nail.

Health Outcome Measures Assessed at baseline, Months 3 and 6:

 Work Productivity and Activity Impairment – Psoriatic Arthritis Questionnaire (ΔWPAI-PsA).

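### The SAP's formula for the PASI scaling component squares the lower-limb scaling score and omits the lower-limb area score

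*SAP*

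**What the plan says.** SAP Appendix 3 Section 5 gives one formula for each PASI clinical sign:

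- Erythema: "PASI_E = 0.1Ah (Eh) + 0.2Au (Eu) + 0.3At (Et) + 0.4Al (El")
- Induration: "PASI_I = 0.1Ah (Ih) + 0.2Au (Iu) + 0.3At (It) + 0.4Al (Il")
- Scaling: "PASI_S = 0.1Ah (Sh) + 0.2Au (Su) + 0.3At (St) + 0.4Sl (Sl")

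The symbols are defined in the same section: "A = area of involvement score; E = erythema", and "S = scaling; h = head". The total PASI formula just above ends in "0.3At (Et + It + St) + 0.4Al (El + Il + Sl"). The rule in words for each body area takes the severity scores "multiplied by the score representing the percentage of this area involved by psoriasis, multiplied by a weighting factor". Protocol Section 7.3.2 gives the same total formula, with Al for the lower limbs.

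The component scores feed an endpoint. SAP Section 3.3.1 lists percent change "in PASI and PASI clinical sign component scores at Month 1, Month 3 and Month 6", for subjects with baseline BSA of at least 3% and baseline PASI above 0. SAP Section 6.3 and Appendix 1 assign it to the mixed model for repeated measures (MMRM), with the baseline value as a covariate.

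**The concern.** The lower-limb term for scaling should be weight × area score × scaling score, as it is for the other two signs. As printed it is 0.4 × Sl × Sl. The area score has dropped out and the severity score enters squared, so the three components no longer add up to the total PASI defined a few lines earlier.

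The lower limbs carry the largest regional weight, 0.4. Under the printed formula, a partial reduction in leg area with leg scaling unchanged leaves the scaling component unchanged. A fall in leg scaling counts by its square. Both the percent change and the baseline covariate in the MMRM would be affected. Appendix 3 is the specification from which programmers work, so an error there can pass straight into the results.

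**Working it through.** **Inputs, all from SAP Appendix 3 Section 5.** Region weights are 0.1 (head), 0.2 (upper limbs), 0.3 (trunk) and 0.4 (lower limbs). Area scores A run from 0 to 6 and severity scores from 0 to 4. The stated range of total PASI is 0.0 to 72.0.

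**Step 1: reproduce the SAP's own maximum.** With every A = 6 and every severity score = 4, total PASI = (0.1 + 0.2 + 0.3 + 0.4) × 6 × (4 + 4 + 4) = 72.0, as stated.

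**Step 2: sum the components at the same maximum.**

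- PASI_E = PASI_I = 1.0 × 6 × 4 = 24.0.
- PASI_S with Al = 24.0, so the sum is 72.0, which agrees with the total.
- PASI_S as printed = (0.1 + 0.2 + 0.3) × 6 × 4 + 0.4 × 4 × 4 = 14.4 + 6.4 = 20.8, so the sum is 24.0 + 24.0 + 20.8 = 68.8, which does not.

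**Step 3: effect on percent change.** The scores here are assumed for illustration, in the order head / upper limbs / trunk / lower limbs.

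*Area falls, scaling unchanged.* Areas go from 1/2/2/3 to 1/1/1/1; scaling is 1/2/2/2 at both visits.

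- With Al, baseline: 0.1×1×1 + 0.2×2×2 + 0.3×2×2 + 0.4×3×2 = 0.1 + 0.8 + 1.2 + 2.4 = 4.5.
- With Al, follow-up: 0.1 + 0.4 + 0.6 + 0.8 = 1.9. Change = (1.9 − 4.5)/4.5 = -57.8%.
- As printed, baseline: 0.1 + 0.8 + 1.2 + 0.4×2×2 = 3.7.
- As printed, follow-up: 0.1 + 0.4 + 0.6 + 1.6 = 2.7. Change = (2.7 − 3.7)/3.7 = -27.0%.

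*Scaling falls, area unchanged.* Areas are 1/2/2/2 at both visits; scaling goes from 2/2/2/3 to 1/1/1/1.

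- With Al: 0.2 + 0.8 + 1.2 + 2.4 = 4.6 falls to 0.1 + 0.4 + 0.6 + 0.8 = 1.9, a change of -58.7%.
- As printed: 0.2 + 0.8 + 1.2 + 3.6 = 5.8 falls to 0.1 + 0.4 + 0.6 + 0.4 = 1.5, a change of -74.1%.

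*Lower limbs only:*

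| Lower-limb scores | With Al | As printed |
|---|---|---|
| Area 3 to 1, scaling 3 at both visits | 3.6 to 1.2: -66.7% | 3.6 to 3.6: 0.0% |
| Area 2 at both visits, scaling 4 to 2 | 3.2 to 1.6: -50.0% | 6.4 to 1.6: -75.0% |

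The error therefore understates improvement when area shrinks and overstates it when scaling fades.

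**Step 4: how general this is.** With lower-limb disease only and non-zero scores at both visits, there are 6 × 4 × 6 × 4 = 576 possible transitions. The two formulas give different percent changes in 528 of them (91.7%). They agree in the remaining 48, where area and scaling change by the same ratio. This counts score combinations; it is not an estimate of how many subjects would be affected.

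**The case against.** The strongest reply is that this is a typographical slip whose meaning is not in doubt. The rule in words, the symbol definitions, the two sister formulas and both total PASI formulas all point to Al, and nothing in either document supports squaring a severity score. A competent programmer might well code it correctly, and the results are wrong only if the term is taken literally. That stands as a limit on the consequence. It does not make the specification right.

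The text was also extracted from a PDF, and some nearby characters are damaged: the word induration is garbled in the same section, and some SF-36 summary-score coefficients lack the decimal points that their neighbours have. A misread letter cannot be fully excluded. However, every other area symbol in the section reads correctly, so an error in the SAP itself is more likely. The source page should be checked.

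The reach is limited too. Only one of three sign components within an other endpoint is affected, and SAP Section 5.1 makes all inference beyond the primary endpoint nominal. If the legs clear completely, both formulas give zero for that term; the missing area score matters for partial change. Percent change is also unaffected when the lower limbs are clear at both visits, or when Al equals Sl at both. The illustrations are constructed subjects and do not forecast the effect on the trial's estimates. All of this bears on how much the error matters and leaves the error in place.

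**Conclusion.** The formula is wrong as written. It contradicts the rest of its own section and the protocol, and its component maxima sum to 3.2 less than the stated total (72.0 − 68.8). In the constructed cases the percent change is off by between 15 and 67 percentage points, in either direction. Those figures rest on assumed scores and on the formula being programmed as printed. The expected effect on the treatment comparison cannot be derived from the documents, because they give no baseline distribution of lower-limb area and scaling.

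Total PASI and its percent change, PASI75, PASI_E, PASI_I and ACR50 are untouched, so the primary conclusion is not at risk. The correction should still be made, because this is the derivation rule for a pre-specified efficacy endpoint.

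**What to change.** In SAP Appendix 3 Section 5, after checking the source page, change the last term of PASI_S to 0.4Al (Sl). Confirm that the derivation program uses Al, whatever the SAP prints. Add a check that PASI_E + PASI_I + PASI_S equals total PASI for every record with complete data. The scores are whole numbers and the weights are multiples of 0.1, so the two sides should agree to within floating-point tolerance. If any output has already been produced from the printed formula, rerun the scaling-component tables.

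The cost is one symbol in the SAP and one line of validation code. Design, sample size, error rate and data collection do not change.

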#### 7.3.2. Psoriasis Area and Severity Index (PASI)

The Psoriasis Area and Severity Index (PASI) quantifies the severity of a subject's psoriasis based on both lesion severity and the percent of body surface area (BSA) affected. PASI is a composite scoring by the investigator of degree of erythema, induration, and scaling (each scored separately) for each of four body regions, with adjustment for the percent of BSA involved for each body region and for the proportion of the body region to

the whole body. The calculation of BSA is described in Section 7.3.3. Note: PASI should only be performed if  $\geq$ 3% of subject's BSA is affected at baseline.

Lesion Severity: the basic characteristics of psoriatic lesions – erythema, induration and scaling – provide a means for assessing the severity of lesions. Assessment of these three main signs is performed separately for four body regions: head and neck, upper limbs, trunk, (including axillae and groin) and lower limbs (including buttocks). Average erythema, induration and scaling are scored for each body region according to a 5-point scale: 0, no involvement; 1, slight; 2, moderate; 3, marked; 4, very marked. Appropriate morphologic descriptors for each severity score are shown below (Table 3).

Table 3.	Component Scoring Criteria for the Psoriasis Area and Severity Index
	(PASI)

(	Component Score Description		
Erythema (E)			
0	No involvement	None; may have residual hyperpigmentation	
1	Slight	Pink or light red	
2	Moderate	Darker pink-red	
3	Marked	Red	
4	Very Marked	Extremely red, "beefy" red	
Induration (I)			
0	No involvement	None	
1	Slight	Minimal elevation relative to normal surrounding skin	
2	Moderate	Easily palpable with rounded edges	
3	Marked	Elevated with hard, sharp borders	
4	Very Marked	Very elevated with very hard, sharp borders	
Scaling	Scaling (S)		
0	No involvement	None	
1	Slight	Mainly fine scale, some lesion partially covered	
2	Moderate	Coarser thin scale, most lesions partially covered	
3	Marked	Coarser thick scale, nearly all lesions covered, rough	
4	Very Marked	Very thick scale, all lesions covered, very rough	

Percent BSA with Psoriasis: the extent (%) to which each of the four body regions is involved with psoriasis is categorized using a non-linear scaling method to a numerical area score according to the following BSA scoring criteria (Table 4).

 Table 4.
 Psoriasis Area and Severity Index (PASI) Area Score Criteria

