Percent Body Surface Area (BSA) with Psoriasis	Area Score
0%	0
>0-9%	1
10-29%	2
30-49%	3
50-69%	4
70-89%	5
90-100%	6
Body Region Weighting: each body region is weighted according to its approximate percentage of the whole body (Table 5).

Body Region	Body Region Weighting
Head and Neck	0.1
Upper Limbs	0.2
Trunk (including axillae and groin)	0.3
Lower Limbs (including buttocks)	0.4

Table 5.	Psoriasis Area and	d Severity Index	(PASI) Lesions	Body Region	Weighting
I abic 5.	1 SUI Iasis I II ca and	a Severity math		Doug Region	······································

In each body region, the sum of the Severity Scores for erythema, inducation and scaling is multiplied by the Area Score and by the Body Region Weighting to provide a body region value, which is then summed across all four body regions resulting in a PASI score as described in the following equation:

$$PASI = 0.1Ah(Eh+Ih+Sh) + 0.2Au(Eu+Iu+Su) + 0.3At(Et+It+St) + 0.4Al(El+Il+Sl)$$

where A = Area Score; E = erythema; I = induration; S = scaling; h = head and neck; u = upper limbs; t = trunk; l = lower limbs.

The PASI score can vary in increments of 0.1 and range from 0.0 to 72.0, with higher scores representing greater severity of psoriasis.

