#### 5.3. Methods to Manage Missing Data

As stated in the protocol, in the primary analysis of the primary endpoint, ACR50 response rate at Month 3, missing values for any reason, e.g., due to a subject dropping from the study or due to the impact of COVID-19 pandemic, will be handled by setting the ACR50 value to nonresponsive. Note that this can be viewed as a composite endpoint in the sense that a response requires the subject completes a visit of interest, e.g., Month 3, and achieves a response per the defined ACR50 response criteria (otherwise it is considered a nonresponse). This method of handling missing response is known as missing response as non-response (MR=NR). This MR=NR approach will be used for all "response-type" endpoints at all timepoints except for the supportive analyses using GMMRM (see Section 5.2.1.2) and Tipping Point Analysis (see Section 5.2.1.3) for ACR50 up to Month 3. Note that if a subject

discontinues from the study at a visit of interest, say Month 3, but the value of the endpoint is not missing at Month 3, the value of the endpoint will be used for Month 3.

For a composite "response-type" endpoints (such as ACR50), if values in any of the components at a timepoint are missing, the component variables that are not missing will be used to determine the response status. If one could not determine the response status in the presence of missing components at the timepoint, then the composite response-type endpoint status is considered as missing and is handled by MR=NR for that timepoint for all of the inferential analyses except for the supportive analyses using GMMRM (see Section 5.2.1.2) and Tipping Point Analysis (see Section 5.2.1.3) for ACR50 up to Month 3.

Repeated measures data for continuous and ordered-categorical (analyzed as continuous) endpoints will be analyzed with MMRM. This model will yield unbiased estimates and valid inferences in the presence of data that is MCAR or missing at random (MAR). Given that subjects who drop out are scheduled to have an end of study evaluation, the more stringent condition of MAR (Rubin, 1987) is believed to be a reasonable assumption. Hence missing values will not be imputed in the routine analysis using the repeated measures model.

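### The SAP makes PASI missing when sign scores are blank in a region with area score 0, although the formula already fixes that region's contribution at 0

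*SAP*

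**What the plan says.** Protocol Section 7.3.2 and SAP Appendix 3, Section 5 build PASI from four body regions. In each region the three sign scores are summed, and the protocol has that sum "multiplied by the Area Score and by the Body Region Weighting to provide a body region value". The SAP then adds: "Any missing component will result in PASI as missing". It does not treat an area score of 0 separately.

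Both documents also say how an uninvolved region is scored. The SAP scale for each sign runs "0, no involvement; 1, slight; 2, moderate; 3, marked; 4, very marked", and the protocol's descriptor for erythema 0 is "None; may have residual hyperpigmentation". All four regions are to be rated: "Assessment of these three main signs is performed separately for four areas of the body". Neither document tells the assessor to skip the signs when the area score is 0.

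What follows from a missing PASI is set elsewhere:

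- **PASI75** is a secondary binary endpoint, and a missing response counts as nonresponse (SAP Sections 5.3 and 6.2.1).
- **Percent change in PASI** and in its sign components is an other endpoint, analysed by MMRM without imputation (SAP Sections 6.2.2 and 6.3).
- **Baseline:** both endpoints need a baseline PASI above 0 (SAP Section 3.2.1, Section 3.3.1 and Appendix 1), which a missing value cannot meet.
- **Composite response-type endpoints** have a general rule in SAP Section 5.3. The components that are present decide the status, and it is missing only if they cannot. ACR50 is the example given; PASI75 is not mentioned.

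**The concern.** A rule that turns an incomplete score into a missing one is normally cautious, because the missing item could have changed the result. Here it also covers a case where the item cannot change the result. A sign score in a region with area score 0 is multiplied by 0.

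If signs are left blank in such a region, the SAP discards a PASI that is known exactly. For PASI75 the discarded value may then be recorded as a failure. In the extreme, a subject with area score 0 in all four regions has a PASI of 0, yet one blank sign would make that subject a PASI75 nonresponder on the literal reading.

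The rule also sits oddly with the rest of Appendix 3. ACR status is kept whenever the available components settle it (Section 1). HAQ-DI tolerates up to two missing domains (Section 2). Joint counts, the enthesitis index and the dactylitis score are estimated from the observed items if more than half are present (Sections 9 to 12). PASI is treated more strictly where nothing needs estimating. At stake are the PASI results that serve the dermatological secondary objective.

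**Working it through.** **Formula.** PASI is the sum over regions of w × A × (E + I + S). The weights w are 0.1, 0.2, 0.3 and 0.4, the area score A runs from 0 to 6, and each sign runs from 0 to 4.

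**The plan's own figure.** With A = 6 and E = I = S = 4 everywhere, PASI = (0.1 + 0.2 + 0.3 + 0.4) × 6 × 12 = 72.0. With zeros everywhere it is 0.0. The stated range of 0.0 to 72.0 is reproduced.

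**A constructed subject.** The scores are invented for illustration. PASI75 is taken as a fall of at least 75% from baseline, which is an assumption because the SAP prints no formula for it.

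| Region (weight) | Baseline A; E, I, S | Value | Follow-up A; E, I, S | Value |
|---|---|---|---|---|
| Head and neck (0.1) | 1; 2, 2, 2 | 0.6 | 1; 1, 0, 1 | 0.2 |
| Upper limbs (0.2) | 2; 2, 2, 2 | 2.4 | 1; 1, 1, 1 | 0.6 |
| Trunk (0.3) | 2; 3, 2, 2 | 4.2 | 1; 1, 1, 0 | 0.6 |
| Lower limbs (0.4) | 3; 3, 2, 2 | 8.4 | 0; blank | 0 |
| PASI | | 15.6 | | 1.4 |

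Whether the blank lower-limb signs are filled with 0, 0, 0 or with 4, 4, 4, the region's value is 0.4 × 0 × (E + I + S) = 0 and PASI is 1.4. Improvement is (15.6 − 1.4) / 15.6 = 91.0%, a PASI75 response. Under the Appendix 3 sentence PASI is missing, and treating missing as nonresponse makes the subject a failure. Had the assessor entered 0, 0, 0, nothing would be missing and both routes would give 1.4.

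The same algebra applies to the sign component scores, which multiply A by a single sign. The lower-limb scaling term is printed with Sl where the pattern of the other two lines implies Al; this reading takes it as Al.

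**Size.** The documents give no rate of blank signs in clear regions, so the effect cannot be computed. As an illustration only, take the PASI75 rates that Protocol Section 1.2.7 reports for the plaque psoriasis study at Week 16 (54.55% on 5 mg BID, 12.50% on placebo). Assume that the same share x of true responders is lost in both arms. The difference becomes (54.55 − 12.50) × (1 − x):

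| Assumed share lost | Difference (points) |
|---|---|
| 0% | 42.1 |
| 2% | 41.2 |
| 5% | 39.9 |
| 10% | 37.8 |
| 20% | 33.6 |

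The ratio of the two rates stays at 54.55 / 12.50 = 4.36 throughout. These rates come from moderate to severe plaque psoriasis, not from this population.

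**The case against.** The strongest objection is that the trigger does not appear in the documents. Zero is a defined sign score, all four regions are to be rated, and the assessors are to be qualified and trained (Protocol Section 7.3). A clear region scored as instructed is complete, and PASI is computed. This stands, and it makes the whole point conditional on blanks that the documents neither describe nor rule out. The CRF is not among them.

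A reader might infer that subjects are lost because a region cleared, hence more often on tofacitinib, with bias against it. The documents do not support that. Clearing a region does not create a missing item, and nothing shows that blanks would differ by arm. A reader might also infer that one uninvolved region at baseline removes a subject. It does so only if its signs are blank. Because baseline PASI is assessed before randomization (Protocol Section 6.2.1), such a loss could not depend on the assigned arm.

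The Section 5.3 composite rule may rescue PASI75: the SAP itself calls PASI a composite scoring, and with area score 0 the status can be determined. That is a fair reading. But the SAP does not say that it overrides the PASI-specific sentence, so two programmers could differ. Section 5.3 covers response-type endpoints only, so it cannot help percent change in PASI or a missing baseline.

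Finally, requiring every component is an ordinary choice, also made for DAS28-3(CRP) in Appendix 3, Section 8. There, however, the terms are added, so a missing one leaves the score unknown. In PASI an area score of 0 makes the signs irrelevant.

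**Conclusion.** The point holds in a limited form. The Appendix 3 sentence discards a PASI that the formula determines exactly when the only blanks are sign scores in a region with area score 0. If that happens after baseline, percent change in PASI loses that visit, although the MMRM still uses the subject's other visits. PASI75 becomes a nonresponse unless Section 5.3 is taken to prevail. If it happens at baseline, the subject leaves the PASI analysis set. That is not far-fetched where it depends on extent of disease: PASI is scored from 3% of body surface, roughly three handprints (Protocol Section 7.3.3), so some regions may well be clear.

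The effect is zero under complete recording, and its frequency otherwise is unknown. The illustrated range rests on assumed shares and on rates borrowed from another population, so it is not evidence of bias in this trial. SAP Section 5.1 treats inference on every endpoint but the primary as nominal, and the ACR50 analysis does not use PASI. This is a free improvement.

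**What to change.** Add to SAP Appendix 3, Section 5:

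> *If the area score of a region is 0, that region contributes 0 to PASI and to each sign component score, and blank sign scores for that region are not counted as missing.*

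Keep the existing rule for any region whose area score is above 0 or is itself missing. Add a clause saying whether PASI75 falls under the composite rule of Section 5.3 and, if so, how that rule fits with the Appendix 3 sentence.

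The cost is a sentence and a clause in the SAP and one line of derivation code. There is no statistical downside, because the exception uses only values that the formula already fixes. It follows the principle that the SAP applies to ACR status, and no primary result changes.
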